8.2. Analysis of Secondary Immunogenicity Endpoints

8.2.1. GMTs of neutralizing Ab titers and GMI from baseline of neutralizing Ab titers against SARS CoV-2 WT and GMTs of serum binding IgG Ab titers and GMI from baseline of IgG titers against SARS CoV-2 S protein and RBD at each collection time point

For continuous variables, summary statistics, Geometric Mean Titer (GMT) and associated 95% CIs, and interquartile ranges will be provided. Listings will also be provided by age group and dose group with a symbol used to indicate participants with prior Covid-19 Infection status. Graphical presentations will be considered as needed.

Immunogenicity of the study vaccine will be assessed through GMTs at each collection time point (day 1) before the booster dose and after the booster dose (Days 8, 15, 29, 85, and 180). GMTs and GMIs from baseline will be summarized with descriptive statistics including a bar chart (on log scale) for each age group and prior Covid-19 infection status versus time.

The GMT will be calculated using the following formula:

$$10^{\left\{\frac{\sum_{i=1}^{n}\log_{10}(t_i)}{n}\right\}}$$

Where $t_1, t_2, ..., t_n$ are *n* observed immunogenicity titers.

The GMI measures the changes in immunogenicity titers or levels within participants (change from baseline in log titers). The GMI will be calculated using the following formula:

$$10^{\left\{\frac{\sum_{i=1}^{n}\log_{10}\left(\frac{v_{ij}}{v_{ik}}\right)}{n}\right\}} = 10^{\left\{\frac{\sum_{i=1}^{n}\log_{10}\left(v_{ij}\right) - \log_{10}\left(v_{ik}\right)}{n}\right\}}$$

where, for *n* participants, v_{ij} and v_{jk} are observed immunogenicity titers for participant *I* at time points *j* and *k*, *k*=*baseline*.

Antibody titers will be summarized at baseline and each postvaccination visit (the number of participants with nonmissing data, median, minimum, maximum, GMT, and 95% CI). Geometric

mean increase and the corresponding 95% CI for the GMI as well as the minimum and maximum fold-rise value will be presented by age group or prior Covid-19 infection, dose group and visit. The 95% CI will be calculated based on the t-distribution of the log-transformed fold-rise values for GMTs and GMIs, then back-transformed to the original scale for presentation.

[figure not shown]
Supporting data listings will be provided for the All Enrolled Set by age group, dose group and participant number.

8.4. Analysis of COVID -19 Incidence-Adverse Event of Special Interest

Proportion of participants with the following will be summarized by dose group:

- 1. Laboratory-confirmed (RT PCR) symptomatic SARS-CoV-2 infection
- 2. Laboratory-confirmed asymptomatic or symptomatic (RT-PCR or N protein seroconversion) SARS-CoV-2 infection
- 3. Laboratory-confirmed severe SARS CoV-2 infection
- 4. Medically attended visits due to laboratory-confirmed SARS-CoV-2 infection
- 5. Hospitalizations or death due to laboratory-confirmed SARS-CoV-2 infection

Frequencies and estimates of the proportion of participants with the above events from study vaccination through the end of the study will be computed by dose group.

9. Safety Analysis

Safety, tolerability, and reactogenicity will be assessed by clinical review of all relevant parameters including solicited and unsolicited AEs, SAEs, AESIs, MAAEs, AEs leading to withdrawal from study participation, safety laboratory test results, vital signs, and physical examination findings.

All safety analyses will be based on Safety Set. All safety analyses will be provided by dose group and age group unless otherwise specified.

9.1. Adverse Events

An AE is defined as any untoward medical occurrence in a participant enrolled into this study regardless of its causal relationship to the IP. This definition includes exacerbations of preexisting conditions. Stable pre-existing conditions which do not change in nature or severity during the study are not considered AEs; however, these should be reported as part of the medical history at screening.

SOC will be displayed in alphabetical order. PT will also be displayed alphabetically within SOC. Percentages will be based upon the number of participants in the Safety Set within each dose group.

Incomplete AE onset date/time and end date will be imputed following the rules below.

Missing Start Dates

If day is missing and month and year are available:

• UK-MMM-YYYY: Assume 01-MMM-YYYY (first day of the month), but if month and year are the same as the first study vaccination month and year, then assume the date of first vaccination.

If day and month are missing and year is available:

• UK-UKN-YYYY: Assume 01-JAN-YYYY (first day of the year), but if year is the same as the first study vaccination year, then assume the date of first study vaccination.

If day, month and year (date) are missing:

• UK-UKN-UNKN: Assume date of first study vaccination.

Missing Stop Dates

If day missing and month and year are available:

• UK-MMM-YYYY: Assume the last day of the month

If day and month are missing and year is available:

• UK-UKN-YYYY: Assume 31-DEC-YYYY

if day, month and year (date) are missing:

• UK-UKN-UNKN: Do not impute and assume ongoing

All AEs will be classified by SOC and PT according to the latest version of the MedDRA.

Unless otherwise specified, AEs will be summarized by dose group based on the Safety Set. A listing of AEs will be provided by age group, dose group and participant number. All events from screening until vaccination will be considered as medical history.

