7.1.2. Concomitant Medications

Concomitant medications are defined as any medications and vaccine (other than study vaccines) taken after the first dose of the study vaccine that were taken:

- Within 6 months of Screening or
- First prior to the dosing and on-going after first dose up to 6 months or
- Within 2 weeks of study vaccination for herbal products, vitamins, minerals, and overthe-counter medications.

Concomitant medications will be listed and summarized in a similar manner to that of prior medications.

For the purpose of inclusion in prior and concomitant medications tables, incomplete start and stop dates will be imputed according to the below rules (where UK, UKN, and UNKN indicate unknown or missing day, month, and year, respectively):

Missing Start Dates

If day is missing and month and year are available:

• UK-MMM-YYYY: Assume 01-MMM-YYYY (first day of the month), but if month and year are the same as the first study vaccination month and year, then assume the date of first vaccination.

If day and month are missing and year is available:

• UK-UKN-YYYY: Assume 01-JAN-YYYY (first day of the year), but if year is the same as the first study vaccination year, then assume the date of first study vaccination.

If day, month and year (date) are missing:

• UK-UKN-UNKN: Assume date of first study vaccination.

Missing Stop Dates

If day missing and month and year are available:

• UK-MMM-YYYY: Assume the last day of the month

If day and month are missing and year is available:

• UK-UKN-YYYY: Assume 31-DEC-YYYY

if day, month and year (date) are missing:

• UK-UKN-UNKN: Do not impute and assume ongoing

(Note - In case of single dose vaccine or treatment, start date may be same as that of end date.)

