9.1.4. Solicited Adverse Event

Solicited AEs are prespecified local and systemic. Solicited AEs will be collected through 7 days following the vaccination (Day 1-7) using eDiary. Solicited AEs with onset during the 7-day solicitation period that continue beyond the 7-day period will be reported as unsolicited AEs.

The following specific solicited adverse events will be used to assess reactogenicity.

Local reactions at injection site:

- Injection Site Pain
- Redness
- Swelling
- Lymphadenopathy (localized axillary, cervical or supraclavicular swelling or tenderness ipsilateral to the vaccination arm)

Systemic reactions:

- Fever
- Headache

- Fatigue
- Myalgia
- Arthralgia
- Chills

The number and percentage of participants with any local solicited AEs, and systemic solicited AEs will be presented for each age group and dose group among participants with eDiary information available.

All solicited AEs local and systemic will be listed by age and participant number. Solicited adverse events reported until 7 days (Day 1 through Day 7) postvaccination will be summarized by maximum severity and by dose group.

Prolonged Solicited AEs that continue beyond day 7 will be reported on the eCRF as Unsolicited AEs and will be listed as such. The number and percentage of participants with prolonged solicited AEs will be presented for each age group (any, any local, any systemic, each solicited AE).

In addition, the duration (in days) of solicited AEs which started within day 1-7 will be summarized by dose group for each age group. The duration for any severity will be calculated as Stop date – Start date + 1, where start date is the first day with AE while stop is the last day with the AE in or beyond the solicited period. The duration of solicited AE with specific severities (mild/moderate/severe, moderate/severe, severe) will be the number of days with the severity.

Currently on the eCRF the investigator can document discrepancy in the severity of AEs on the eDiary, if:

- The participant does not report the severity of the event in the eDiary or
- The investigator judges that the participant over- or underestimated the severity of the event

When available the severity provided by the investigator will be used instead of the eDiary grading to generate the summaries of solicited events.

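### SAP date imputation ignores a recorded stop date and leaves imputed stops uncapped, so an event or medication that ended before vaccination can be placed on Day 1 and some reaction durations overstated (minor)

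*SAP*

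**What the plan says.** SAP 9.1 (Adverse Events) sets the rules for incomplete onset dates. If only the day is missing, the first of the month is used, "but if month and year are the same as the first study vaccination month and year, then assume the date of first vaccination". With both day and month unknown, 1 January is used unless the year is the vaccination year, in which case the vaccination date is used. If everything is missing: "UK-UKN-UNKN: Assume date of first study vaccination".

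For stop dates the same section gives "UK-MMM-YYYY: Assume the last day of the month", "UK-UKN-YYYY: Assume 31-DEC-YYYY" and, when nothing is known, "UK-UKN-UNKN: Do not impute and assume ongoing". No limit at death, last contact or study exit is stated.

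SAP 7.1.2 applies the same rules to medications, for deciding inclusion in the prior and concomitant tables. Its year-only clause reads "but if year is the same as the first study vaccination year, then assume the date of first study vaccination".

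Two further sentences matter. SAP 9.1 ends with "All events from screening until vaccination will be considered as medical history". SAP 9.1.4 defines the length of a solicited reaction: "The duration for any severity will be calculated as Stop date – Start date + 1", where the stop may lie beyond Day 7.

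**The concern.** Placing an onset of unknown timing on the day of vaccination is a common and cautious convention. It stops being cautious when the record already shows that the event was over before vaccination. The imputed start then follows the recorded stop, which is impossible, and the event can be counted as occurring after vaccination.

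The SAE and MAAE tables in SAP 9.1.7 and 9.1.8 select on onset date (Days 1-28 and Days 1-180), and the percentages with SAEs and MAAEs from vaccination onward are primary endpoints. Two programmers could build different tables from the same text. One would apply the medical-history sentence first and exclude the event. The other would impute first and count it. The wording on collection periods does not settle the matter, because SAP 9.1.7, 9.1.8 and 9.1.11 say that SAEs, MAAEs and deaths are summarised from consent.

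The missing cap is a separate, smaller problem. A stop date moved to month end or to 31 December can lie after the participant has left the study, and it feeds directly into a duration.

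**Working it through.** **Inputs.** The date rules are in SAP 9.1 and 7.1.2. Study day on or after injection is date minus injection date plus 1, and before injection it is the plain difference (SAP 4). Duration is from SAP 9.1.4. Screening of up to 14 days and 30 participants per dose group are from SAP 3.1. The Day 180 window of ±7 days is from the schedule in SAP 15.1. All calendar dates below are assumed for illustration.

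**1. An SAE that ended before vaccination.** Vaccination 20 Jul 2022; onset UK-JUL-2022; recorded stop 12 Jul 2022.
- Month and year match, so the imputed start is 20 Jul, study day 20 − 20 + 1 = 1.
- The recorded stop is on study day 12 − 20 = −8.
- Stop − start + 1 = 12 − 20 + 1 = −7 days.

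If the medical-history sentence is applied first, using the recorded stop, the event is excluded. If imputation is applied first, it enters the Day 1-28 and Day 1-180 tables. The SAP does not give the order.

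**2. A medication that ended before vaccination.** Same vaccination date (day 201 of the year); start known only as 2022; stop 10 Mar 2022 (day 69). The imputed start is 20 Jul, and stop − start + 1 = 69 − 201 + 1 = −131 days. A program that classifies on start date would show it as concomitant.

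**3. Size of one misplaced participant.** 0/30 = 0% (exact 95% CI 0 to 11.6%) becomes 1/30 = 3.3% (0.1 to 17.2%).

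**4. Which branch of the rule would apply.** Take every vaccination date in a year and onsets 1 to 14 days earlier: 365 × 14 = 5,110 pairs. Each month boundary is crossed by 14 + 13 + … + 1 = 105 pairs.
- Same month as vaccination: (5,110 − 12 × 105)/5,110 = 3,850/5,110 = 75.3%.
- Same year: (5,110 − 105)/5,110 = 5,005/5,110 = 97.9%.

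These are calendar shares. They show that a partial onset date from screening would usually meet the vaccination-date branch. They do not say how often partial dates occur.

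**5. Duration of a solicited reaction.** Onset 3 June.
- Stop known to the month (June): 30 − 3 + 1 = 28 days.
- Stop known only to the year: 28 + 31 + 31 + 30 + 31 + 30 + 31 = 212 days.

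If 3 June is Day 2 (vaccination 2 June), Day 180 is 28 November, while 31 December is Day 213, past the upper visit limit of Day 187.

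For a reaction that truly runs from Day 2 to Day 10 (9 days):

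| Vaccination date | Month-only stop | Year-only stop |
|---|---|---|
| 20 Jul 2022 | 11 days | 164 days |
| 20 Jun 2022 | 10 days | 194 days |

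Over all 2022 vaccination dates, a month-only stop adds 14.7 days on average (range 0 to 30). A year-only stop adds 182 days on average (range 0 to 364) and falls after Day 187 for 51% of dates.

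**6. What a cap does.** In the 3 June example with study exit on 28 November (day 332; 3 June is day 154), the capped duration is 332 − 154 + 1 = 179 days. It stays within follow-up but is still an imputed value, so the number of such values should be reported.

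**The case against.** The strongest reply is that SAP 9.1 already classes pre-vaccination events as medical history, and an event with a recorded stop before vaccination is known to be pre-vaccination without any imputation. Protocol 6.1.1.2 also collects nonserious events only from vaccination, which leaves few candidates: mainly SAEs, MAAEs summarised from consent under SAP 9.1.8, and any pre-dose event entered because the schedule marks adverse events at Screening. SAEs are reported within 24 hours of site awareness, so an unknown onset day beside a known stop day would be unusual. Eligibility is reassessed on Day 1, so some of these participants might not be vaccinated. All of this narrows the exposure. It does not settle the order of the two rules or supply the missing check.

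On duration, Days 1-7 come from a daily eDiary reviewed at Day 8. Only reactions continuing past Day 7 move to the eCRF, where a partial stop can arise. Severity-specific durations are counts of days, and fully missing stops are not imputed. These limits stand.

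Some stronger readings are tempting but not supported:
- An MAAE with a year-only onset first learned at Day 180 would be placed on Day 1. That is the cautious convention for unknown timing, and a stop-date check would normally leave it unchanged.
- An earlier COVID-19 booster dated only by year might seem to run to 31 December. The note closing SAP 7.1.2 allows start and end to coincide for a single-dose vaccine, and Protocol 5.8.1 makes administration dates a minimum recording requirement.
- A group mean duration beyond follow-up would need nearly every record to be affected.

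**Conclusion.** The defect is real and minor. As written, the rules can produce a start after the recorded stop, and a duration longer than follow-up. The first conflicts with the medical-history sentence in the same section.

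A reader might infer that 75% or 98% of screening-period events become Day 1 events. The documents do not support that: these are calendar shares, and both the medical-history sentence and the collection window stand in the way. The supported statement is that one affected participant moves a full dose group of 30 by 3.3 points. How many would be affected is unknown, because the documents give no count of partial dates; it is probably small.

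For medications the effect is limited to whether a drug is tabulated as prior or concomitant. The duration effect is limited to any-severity durations of prolonged solicited reactions with a partial eCRF stop. One such record could distort a group's maximum and noticeably shift its mean. The 212-day figure requires a year-only stop and the assumed 3 June onset, and it reads the general stop rule of SAP 9.1 as applying to SAP 9.1.4, which nothing there excludes.

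**What to change.** Add to SAP 9.1 and, for start dates, to SAP 7.1.2:

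1. Impute the start to the vaccination date only if the stop date is missing, ongoing, or could be on or after vaccination. If the recorded stop is before vaccination, treat the event as medical history or the medication as prior. State that this takes precedence over imputation.
2. An imputed start may not be later than the recorded stop.
3. Cap an imputed adverse-event stop date at the earliest of death, study exit or last contact. Report the number of imputed durations beside the duration summary.

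Records with an imputed stop should stay in the duration summary. Only prolonged reactions are exposed, so removing those records would selectively drop long durations and bias the summary downward.

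The cost is a few sentences in the SAP and a few lines of programming. No new data are needed.

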9.1.1. Relationship of Adverse Events to Study Drug

Investigators will not be required to assess the causality of solicited AEs if the onset is during the solicitation period.

The investigator will determine the causal relationship between the study vaccine and the AE for all unsolicited AEs, SAE, MAAE and AESIs. The relationship of unsolicited AEs to the study vaccine (Yes, No) will be captured on the eCRF.

The number and percentage of participants along with the frequency of AEs (unsolicited AEs and SAEs) by SOC, PT, and relationship will be produced.

A participant with 2 or more AEs within the same SOC or PT level but different relationship will be counted only once in the level using the related incident. If the causality is missing, then a "missing" category will be included in the summary.

9.1.2. Severity of Adverse Event

The severity of AEs (mild, moderate, severe) will be captured on the eCRF. Adverse events (unsolicited AEs, solicited AEs, and SAEs) will be summarized including the number of

participants and percentages by dose group, as well as by SOC, PT, and severity. If the severity is missing, then a "missing" severity category will be included in the summary. A participant with 2 or more AEs within the same SOC or PT level but different severity will be counted only once at the most severe level.

9.1.3. Outcome of Adverse Event

The outcome of an AE will be assessed as at the time of last observation per the following categories:

- Fatal
- Not Recovered/ Not Resolved
- Recovered/Resolved
- Recovered/Resolved with sequelae
- Recovering/Resolving
- Unknown

The number and percentage of participants along with the frequency of adverse events (unsolicited, AESIs, MAAEs and SAEs) will be summarized by SOC, PT, and outcome.

A participant with 2 or more AEs within the same SOC or PT level but different outcome will be counted only once with higher outcome grading.

9.1.4. Solicited Adverse Event

Solicited AEs are prespecified local and systemic. Solicited AEs will be collected through 7 days following the vaccination (Day 1-7) using eDiary. Solicited AEs with onset during the 7-day solicitation period that continue beyond the 7-day period will be reported as unsolicited AEs.

The following specific solicited adverse events will be used to assess reactogenicity.

Local reactions at injection site:

- Injection Site Pain
- Redness
- Swelling
- Lymphadenopathy (localized axillary, cervical or supraclavicular swelling or tenderness ipsilateral to the vaccination arm)

Systemic reactions:

- Fever
- Headache

- Fatigue
- Myalgia
- Arthralgia
- Chills

The number and percentage of participants with any local solicited AEs, and systemic solicited AEs will be presented for each age group and dose group among participants with eDiary information available.

All solicited AEs local and systemic will be listed by age and participant number. Solicited adverse events reported until 7 days (Day 1 through Day 7) postvaccination will be summarized by maximum severity and by dose group.

Prolonged Solicited AEs that continue beyond day 7 will be reported on the eCRF as Unsolicited AEs and will be listed as such. The number and percentage of participants with prolonged solicited AEs will be presented for each age group (any, any local, any systemic, each solicited AE).

In addition, the duration (in days) of solicited AEs which started within day 1-7 will be summarized by dose group for each age group. The duration for any severity will be calculated as Stop date – Start date + 1, where start date is the first day with AE while stop is the last day with the AE in or beyond the solicited period. The duration of solicited AE with specific severities (mild/moderate/severe, moderate/severe, severe) will be the number of days with the severity.

Currently on the eCRF the investigator can document discrepancy in the severity of AEs on the eDiary, if:

- The participant does not report the severity of the event in the eDiary or
- The investigator judges that the participant over- or underestimated the severity of the event

When available the severity provided by the investigator will be used instead of the eDiary grading to generate the summaries of solicited events.

The percentage of eDiary days completed will be summarized by dose and age group. A day is considered completed in the eDiary if it was entered by the participant or the investigator. The percentage of completed days will be calculated as follows:

(SumSymp/(7*NumSymp*ExpSubj))*100

SumSymp is the sum of the total number of days completed for a specific symptom across all symptoms and exposed subjects. NumSymp is the number of symptoms and ExpSubj is the number of exposed subjects.

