3.1 Study Design

This Phase 1 study will evaluate the safety, reactogenicity, and immunogenicity of the CV2CoV vaccine in SARS-CoV-2 seropositive healthy adult participants. The study will be conducted in 5 sequential cohorts with dose escalation from 2 μg to 20 μg. A total of up to approximately 180 healthy adult participants will be enrolled, 30 per dose group as indicated in Table 3-1. The 30 participants will be distributed between the younger (≥18 to <65 years old) and older (≥65 years old) age groups, with a minimum of 10 and a maximum of 20 participants in each age group. There will be 3 sentinel participants in each age group within each dose group. A study design schematic is provided in Figure 3-1.

Table 3-1 CV2CoV Study Cohorts, Dose Groups, and Dose Levels

Cohort	Dose Group	Dose Level	Younger Adults ≥18 to <65 Years of Age	Older Adults ≥65 Years of Age	Total Dose Group Sample Size
1	1a	2 μg	$10 \le n \le 20$	$10 \le n \le 20$	30
	1b	4 μg	$10 \le n \le 20$	$10 \le n \le 20$	30
2	2	8 μg	$10 \le n \le 20$	$10 \le n \le 20$	30
3	3	12 μg	$10 \le n \le 20$	$10 \le n \le 20$	30
4	4	16 µg	$10 \le n \le 20$	$10 \le n \le 20$	30
5	5	20 μg	$10 \le n \le 20$	$10 \le n \le 20$	30

Note: The first 3 participants enrolled in each age group within each dose group will be sentinel participants.

The screening period will be up to 14 days, study vaccine administration will occur on Day 1, and participants will have approximately 180 days (6 months) of follow-up after study vaccine administration. Study assessments will be performed in an outpatient setting at qualified study sites.

The study will be open-label. Participants in all cohorts will be screened for eligibility up to 14 days before enrollment. Participants will receive study vaccine according to their cohort (Table 3-1), dose group, and age group; and study visits will proceed according to the SOE (Table 13-1). Participants will be sequentially enrolled to the dose level assigned to their cohort.

Enrollment in each dose cohorts and the progression from vaccination in younger to older adult participants will be staggered based on SRT data review will progress as described in Section 7.8. Holding rules for dosing are described in Section 5.9.

[figure not shown]

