6.1.1.2.1 Assessment of Severity

The severity, or intensity, of an AE refers to the extent to which an AE affects the participant's daily activities.

Solicited AEs will be graded in intensity by the participant. The investigator will assess the maximum intensity that occurred over the duration of the event for all unsolicited AEs, including SAEs, recorded during the study. The assessment will be based on the investigator's clinical judgment.

The intensity of the following solicited events will be assessed as described in Table 6-1.

Table 6-1 Intensity Scales for Solicited Symptoms

	1	T
.	Intensity	
Event	Grade	Parameter
Pain at administration site	0	None
	1	Mild: Any pain neither interfering with nor preventing normal
		everyday activities
	2	Moderate: Painful when limb is moved and interferes with
		everyday activities
	3	Severe: Significant pain at rest. Prevents normal everyday
D. I	0	activities
Redness at administration site	0	<2.5 cm 2.5 – 5 cm
	1	2.3 – 3 cm 5.1 – 10 cm
	2	
	3	>10 cm
Swelling at administration site	0	<2.5 cm
	1	2.5 – 5 cm and does not interfere with activity
	2	5.1 – 10 cm or interferes with activity
	3	>10 cm or prevents daily activity
Lymphadenopathy ^a	0	None
	1	Mild: No interference with activity
	2	Moderate: Some interference with daily activity
1	3	Severe: Prevents daily activity
Temperature ^b	0	<38.0°C or <100.4°F
	1	38.0 – 38.4°C or 100.4 – 101.1°F
	2	38.5 – 38.9°C or 101.2 – 102.0°F
	3	>38.9°C or >102.0°F
Headache	0	Normal
	1	Mild: Headache that is easily tolerated
	2	Moderate: Headache that interferes with normal activity
	3	Severe: Headache that prevents normal activity
Fatigue	0	Normal
	1	Mild: Fatigue that is easily tolerated
	2	Moderate: Fatigue that interferes with normal activity
	3	Severe: Fatigue that prevents normal activity
Myalgia	0	Normal
	1	Mild: No interference with daily activity
	2	Moderate: Interferes with daily activity
	3	Severe: Prevents daily activity
Arthralgia	0	Normal
	1	Mild: No interference with daily activity
	2	Moderate: Interferes with daily activity
	3	Severe: Prevents daily activity
Chills	0	None
	1	Mild sensation of cold; shivering; chattering of teeth
	2	Moderate tremor of the entire body; narcotics indicated
	3	Severe or prolonged, not responsive to narcotics

a. Defined as localized axillary, cervical or supraclavicular swelling or tenderness ipsilateral to the vaccination arm.

b. Refer to Section 6.1.4 for the definition of fever.

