6.1.1.3 Reporting Adverse Events

All AEs reported or observed during the study will be recorded on the AE page in the eCRF. Information to be collected includes, but is not limited to, the following:

- Event term
- Investigator-specified assessment of severity and causality to IP
- Seriousness/grade
- Time of onset of the event
- Time of resolution of the event
- Any required treatment or evaluations
- Outcome

Adverse events resulting from concurrent illnesses, reactions to concurrent illnesses, reactions to concurrent medications, or progression of disease states must also be reported. All AEs will be followed to adequate resolution. MedDRA will be used to code all AEs.

Any medical condition that is present at the time that the participant is screened but does not deteriorate should not be reported as an AE. However, if it deteriorates at any time during the study, it should be recorded as an AE.

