7.1 Statistical Hypothesis

There is no hypothesis testing in this study; where statistical methods are applied, the emphasis will be on estimation with 95% CIs.

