7.2 Sample Size Determination

The sample size is based on clinical considerations to inform dose regimen decisions for continued clinical development.

Approximately 180 participants will be enrolled in this Phase 1 study, with 6 dose-level cohorts each comprising 2 age groups. With 30 participants in each cohort, there is a 78.5% probability to observe at least 1 AE if the incidence rate is 5% and a 95.8% probability to observe at least 1 AE if the incidence rate is 10%. With 30 participants in each cohort, a 10% unevaluable rate for immunogenicity results, and a standard deviation of 0.45 for log₁₀-transformed increase from Day 1, the ratio of the upper limit of a 2-sided 95% CI and the point estimate of GMI is 1.5.

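### SAP 9.1.4 lets an investigator who knows the dose overrule the participant's solicited-AE grade, contrary to protocol 6.1.1.2.1, so severity results by dose may reflect knowledge of dose and no planned output would show it

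*SAP*

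**What the plan says.** Protocol section 6.1.1.2.1 divides the grading between two people. For solicited events, "Solicited AEs will be graded in intensity by the participant". For the rest, "The investigator will assess the maximum intensity that occurred over the duration of the event for all unsolicited AEs, including SAEs". The section gives no rule under which the investigator may replace a diary grade.

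SAP section 9.1.4 describes an eCRF entry where the investigator can record a severity that differs from the eDiary. It has two triggers: the participant gave no severity, or the investigator considers that the participant over- or underrated the event. Where such an entry exists, "the severity provided by the investigator will be used instead of the eDiary grading to generate the summaries of solicited events". Otherwise the diary grade stands.

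On blinding, protocol section 3.1 states: "The study will be open-label". Protocol section 5.6 blinds only the immunogenicity laboratories.

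One protocol passage points the other way. Section 6.1.1.3 lists, among the items collected for adverse events, "Investigator-specified assessment of severity and causality to IP". It does not say that this replaces a diary grade.

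SAP section 13 records changes in the planned analysis as not applicable.

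**The concern.** Filling a blank grade and overruling a reported one are different acts, and the SAP treats them alike. The second is discretionary, works in both directions and has no stated criterion. The person exercising it knows the dose and can know that Grade 3 counts matter to the study's progress.

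Most of the systemic items, and injection-site pain, are graded in protocol Table 6-1 largely by discomfort or interference with activity, which the participant experiences directly. If doubtful reports are downgraded more readily at some doses than at others, a dose trend in severity can be flattened or created.

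The SAP plans no count of changed grades and no summary on the participant's own grades. A reader of the study report could not tell whether this had happened.

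**Working it through.** **1. Which results depend on the grade**

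- *Primary solicited-event endpoint* (protocol Table 2-1; SAP sections 2.1 and 8.1.2): percentage of participants in whom the event occurs on Days 1 to 7. The definition contains no grade, so a change among Grades 1, 2 and 3 alters it by 0. Only a change to or from Grade 0 could move it, and the SAP neither allows nor forbids that.
- *Severity summaries* (SAP section 9.1.4): maximum severity by dose group, and duration by severity. These change directly with the grade.
- *Holding rules 1g and 2a* (protocol Table 5-2) *and the Bayesian model* (protocol Appendix 13.3): these use Grade 3 solicited events. SAP 9.1.4 speaks only of summaries, and neither document says which grade these tools receive.

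**2. The plan's own safety figures** (protocol section 7.2, n = 30 per dose group)

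P(at least one event) = 1 − (1 − p)^30.
- p = 5%: 1 − 0.95^30 = 78.5% (stated 78.5%).
- p = 10%: 1 − 0.90^30 = 95.8% (stated 95.8%).

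Both reproduce. The plan gives no rate at which diary grades are expected to be overruled, so no single bias figure can be derived.

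**3. Effect of one regrade on a Grade 3 rate**

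The change is 1/n, provided the regraded event was that participant's only one at Grade 3 for the item summarised.
- Full dose group: 1/30 = 3.3 points.
- One age group of 10 to 20: 1/20 = 5 points to 1/10 = 10 points.
- Two downgrades from 8/30 = 26.7% (exact 95% CI 12.3 to 45.9) give 6/30 = 20.0% (7.7 to 38.6).

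**4. Conditional check: if the overruled grade also fed the Bayesian model**

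This is an assumption. I used the Appendix 13.3 model, logit p(d) = α + β·log(d/12), without the age effect, with the stated 80/20 mixture prior, numerical integration, and the zero count at 2 µg replaced by 1 as the appendix describes.

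Table 13-2, scenario 2, P(rate at next dose > 30%):

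| Current dose | Events/30 | Recomputed | Stated |
|---|---|---|---|
| 4 µg | 4 | 0.24 | 0.236 |
| 8 µg | 6 | 0.44 | 0.437 |
| 12 µg | 8 | 0.65 | 0.645 |
| 16 µg | 15 | 0.99 | 0.994 |

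The next-dose column reproduces closely. The current-dose value at 4 µg does not (about 0.000 against 0.050), but it is not used here.

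Changing only the count at 12 µg, P(rate at 16 µg > 30%) is 0.65 with 8 events, 0.53 with 7 and 0.41 with 6. Two downgrades cross the 50% guide; one does not.

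**The case against.** **The study is descriptive.** Protocol section 7.1 says: "There is no hypothesis testing in this study; where statistical methods are applied, the emphasis will be on estimation with 95% CIs". No test can be distorted, no overrule rate is given, and so no bias is demonstrated. This stands as a limit on the claim. What remains is an exposure that the outputs cannot rule out.

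**A reader might infer that the primary endpoint is at risk.** The documents do not support that. The endpoint is occurrence, and regrading among Grades 1 to 3 leaves it unchanged.

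**A reader might infer that one regrade among sentinels decides escalation.** With 0/3 at 2 and 4 µg, the model gives P(rate at 12 µg > 30%) of about 0.54 for 1/3 at 8 µg and 0.32 for 0/3. That example is a knife edge. The prior alone already lies above the guide: logit(0.30) = −0.847, so the probability is 0.8 × 0.5 + 0.2 × Φ(−0.4055 + 0.8473) = 0.8 × 0.5 + 0.2 × 0.671 = 0.53. Pooling both age groups' sentinels (six per dose), 1/6 against 0/6 at 8 µg gives about 0.42 against 0.26, both below 0.5. Appendix 13.3 itself urges caution at small numbers, and protocol section 5.9 rests the decision on medical judgement. For rule 2a, 2/3 against 1/3 would change whether a hold is triggered, not what the review concludes, and only if the overruled grade is the one used.

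**Investigator severity is already in the protocol** (section 6.1.1.3). True, so the protocol is not silent. But that general list does not cancel the specific assignment in 6.1.1.2.1.

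**Participants also know their dose, and some items are measured.** Both points stand. Participant grading removes only the investigator's added layer, and the redness and temperature cut-offs leave less room for judgement.

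**Conclusion.** The point holds for the severity results under the primary reactogenicity objective, and no further. The SAP changes who grades a disputed solicited event, the new grader knows the dose, the change is not declared, and no output would make selective regrading visible.

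The size is 3.3 points on a full dose group's Grade 3 rate per participant regraded into or out of Grade 3. The direction and frequency are unknown.

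An effect on holding rules or escalation rests on the unstated assumption that the same overruled grade is used there. Under it, two downgrades in the protocol's own scenario 2 move the 16 µg probability from 0.65 to 0.41. The silence on this needs resolving whatever the answer.

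This is a cheap improvement worth making, not a flaw that invalidates the safety analysis.

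**What to change.** - Reconcile protocol sections 6.1.1.2.1 and 6.1.1.3 with SAP section 9.1.4.
- Base the main severity and duration summaries on the participant's eDiary grade, using the investigator's grade only where the diary grade is missing.
- Add a sensitivity summary on investigator grades.
- Add a table of regrades by dose group and direction, separating blank grades filled from reported grades overruled. Say whether a change to or from Grade 0 is possible.
- State which grade feeds rules 1g and 2a and the Bayesian model.
- Record any departure kept from the protocol in SAP section 13.

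The cost is SAP wording and about two extra tables. The eDiary grade and the eCRF discrepancy entry should already supply the data, provided both are retained. The downside is that a genuine diary entry error stays in the main table and is corrected only in the sensitivity summary.
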